13.1 Study Design/Endpoints

Primary Endpoints:

For the phase I portion of the trial:

A conventional algorithm (3+3 design) will be used to identify the MTD, escalating on 0/3 or 1/6

DLTs, and de-escalating if two DLTs are encountered. The MTD will be the highest dose level at which $\leq 1/6$ subjects experience a DLT. If dose level 1 is discovered to be intolerable (with 2/3 or $\geq 2/6$ subjects experiencing a DLT), the trial will be discontinued. The probabilities of escalation if the true but unknown DLT rates are 10, 20, 30, 40, and 50% are 91, 71, 49, 31, and 17%, respectively.

Data will be summarized using descriptive statistics for continuous variables and frequencies, percentages for discrete variables, and presented by dose group, as appropriate.

For the phase II portion of the trial:

Primary Endpoint:

For the phase II portion of the trial, the primary endpoint will be PFS, defined as the time from study enrollment until the identification of disease progression by RECIST 1.1 criteria or death. Patients who have not experienced an event of interest by the time of analysis will be censored at the date they are last known to be progression-free.

Power is based on the Wald test of the log failure rate. We assume uniform accrual for 12 months, 12 additional months of follow-up, and a null median PFS of 10 months. A sample of 25 subjects, with 12 observed PFS events, will have 85% power to detect an alternative median PFS of 20 months (hazard ratio = 2), The design assumes a one-sided, type-I error of 10%. The null median PFS of 10 months will be rejected if the observed median PFS is at least 14.5 months.

Secondary Endpoints:

Overall response rate (ORR) will be assessed by RECIST 1.1 criteria and will be graded as complete response, partial response, stable disease and progressive disease. Overall survival (OS) will be defined as the time from study enrollment to death from any cause. Patients who are alive at the time of analysis will be censored at the date of last vital status.

Toxicity will be assessed using the CTCAE version 4.03.

Exploratory Endpoints:

Data from correlative studies will be summarized using descriptive statistics. Associations between MAPK signaling, TAMs, and immune infiltrates will be compared to clinical outcome and will be summarized by descriptive methods and may be explored graphically.

Additionally, tumor DNA levels obtained from the serial collection of cfDNA samples will be examined to explore whether clinical outcome correlates to fluctuations following the administration of LY3022855 combination therapy.

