13.2 Sample Size, Accrual Rate and Study Duration

The planned sample size is between six and 18 patients in the phase I portion of the trial, and 25

patients in the phase II portion of the trial, for a total of 31 to 43 patients. The planned accrual rate is approximately 5 patients per quarter. Up to an additional one year of follow-up will be required for the last participant accrued to observe the patient's response and survival following therapy, for a total study length of about four years. Participants will be identified via targeted NextGen sequencing using the DFCI/BWH OncoPanel or another CLIA-certified method for genotyping.

Table 26: Accrual Targets					
Ethnic Category	Sex/Gender				
Zumie Cutegory	Females		Males		Total
Hispanic or Latino	0	+	1	=	1
Not Hispanic or Latino	15	+	27	=	42
Ethnic Category: Total of all subjects	15	+	28	=	43
Racial Category					
American Indian or Alaskan Native	0	+	1	=	1
Asian	0	+	0	=	0
Black or African American	0	+	0	=	0
Native Hawaiian or other Pacific Islander	0	+	0	=	0
White	15	+	27	=	42
Racial Category: Total of all subjects	15	+	28	=	43

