13.3 Analysis of Primary and Secondary Endpoints

The primary and secondary analyses will include all eligible patients who started assigned therapy. The phase II evaluations will not include the patients enrolled to the phase I portion of this trial. The exception to this includes the planned analysis of toxicity data, which will include all patients who received study drug regardless of eligibility.

Overall response rate will be presented with a 90% exact binomial confidence interval. For a sample of size 25, the confidence interval will be no wider than 0.35. The distributions of overall survival and progression-free survival will be described using the method of Kaplan-Meier. Median PFS and OS will be summarized with 90% confidence intervals estimated using log (-log(endpoint)) methodology.

In the event that there are missing data points, no imputation of the missing data will be conducted.

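### The fixed 14.5-month cut-off equals the phase II Wald test only at 12 events; the rule performs close to plan, but section 13.1 should fix the test, the estimator and the analysis time

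*Combined protocol and SAP*

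**What the plan says.** All in the combined protocol and SAP.

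- Section 13.1, test: "Power is based on the Wald test of the log failure rate". The stated type I error is one-sided 10%.
- Section 13.1, timing: "We assume uniform accrual for 12 months, 12 additional months of follow-up, and a null median PFS of 10 months".
- Section 13.1, size and power: "A sample of 25 subjects, with 12 observed PFS events, will have 85% power to detect an alternative median PFS of 20 months".
- Section 13.1, decision: "The null median PFS of 10 months will be rejected if the observed median PFS is at least 14.5 months".
- Section 13.2, accrual: the planned "rate is approximately 5 patients per quarter". Follow-up: "Up to an additional one year of follow-up will be required for the last participant accrued". Section 14 refers back to 13.2 for when outcome data are mature.
- Section 13.3, method: "The distributions of overall survival and progression-free survival will be described using the method of Kaplan-Meier", and "Median PFS and OS will be summarized with 90% confidence intervals". It names no test.

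Section 13.1 does not say which estimate of the median the 14.5 months applies to, how an unreached median counts, or on what date the rule is applied. No section triggers the analysis at the 12th event.

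**The concern.** The Wald test of a log failure rate has standard error 1/√d, where d is the number of events, so its cut-off on the median scale moves with d. A fixed 14.5 months can equal that test at one event count only. If the count that produced 14.5 is the one expected under the alternative, the threshold does not match the test under the null, which is where type I error is defined. This sentence decides the phase II primary question. The power is justified with one procedure and the decision is taken with another, and the points left open could be settled after single-arm, open-label data have been seen.

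**Working it through.** **Inputs.** From 13.1: n = 25, null median 10 months, alternative 20 months, one-sided 10% (z = 1.2816), accrual A = 12 months, further follow-up F = 12 months, 12 events. From 13.2: 5 patients per quarter, so 25 patients take 15 months (sensitivity case). Assumed: exponential PFS, which the Wald power already implies, and no dropout, since none is given.

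**1. Reproducing the plan.**
- Cut-off at d events = 10·exp(1.2816/√d). At d = 12 this is 14.48, which rounds to 14.5.
- Power = Φ(ln 2·√d − 1.2816). At d = 12 this is Φ(2.401 − 1.282) = 86.9%; at d = 11.51 it is 85.8%. Both are close to the stated 85%.

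So the cut-off and the power agree with each other at about 12 events.

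**2. Expected events at the planned cut.** With L = ln 2/median, P(event) = 1 − [exp(−L·F) − exp(−L·(A+F))]/(A·L).
- Median 10: 1 − (0.4353 − 0.1895)/0.8318 = 0.7045, times 25 = 17.6 events.
- Median 20: 1 − (0.6598 − 0.4353)/0.4159 = 0.4602, times 25 = 11.5 events.
- With A = 15: 18.2 and 12.1 events.

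Twelve is therefore about the count under the alternative. Under the null, 13 or more events occur in 98.5% of trials (binomial, 25 and 0.7045).

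**3. The Wald cut-off under the null.** At d = 17.6 it is 10·exp(1.2816/√17.6) = 13.57 months. The nominal level of a fixed 14.5 is 1 − Φ(ln 1.45·√d): 9.9% at d = 12 but 5.9% at d = 17.6.

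**4. Operating characteristics.** Simulation, 400,000 trials per setting, cut 12 months after last accrual (type I error / power):

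| Rule | 12-month accrual | 15-month accrual |
|---|---|---|
| 14.5 on the exponential median | 6.6% / 87.5% | 6.1% / 88.0% |
| 14.5 on the Kaplan-Meier median, unreached = at least 14.5 | 9.2% / 86.1% | 9.1% / 86.2% |
| Wald test at the observed d | 8.5% / 90.1% | 8.6% / 91.0% |

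**5. Where the shortfall on the exponential median comes from.** The Wald test at the observed d already sits at 8.5%, because of the normal approximation. Fixing the cut-off accounts for only the step from 8.5% to 6.6%, about 2 points. Stopping at exactly 12 events would not restore 10% either: total PFS time is then gamma distributed, and P(χ² with 24 df ≥ 2·12·1.45 = 34.8) = 7.1%.

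**6. How often the two rules part.** Wald against Kaplan-Meier 14.5, 12-month accrual:
- Null: 5.6% of trials (Wald alone rejects 2.5%, Kaplan-Meier alone 3.1%).
- Alternative: 7.2% (Wald alone 5.6%, Kaplan-Meier alone 1.6%), a net 4.0 points of power.
- With 15-month accrual: 6.0% and 7.8%.

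**7. Unreached medians.** At a true median of 20 months the Kaplan-Meier median is unreached in 39% of trials. In none of these is the longest observed time below 14.5 months, so counting them as success is sensible. Requiring a numerical median would leave about 86 − 39 = 47% power.

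**8. Departures from the plan's assumptions** (Wald v Kaplan-Meier 14.5, type I error / power):
- Weibull shape 0.8: 14.1% / 84.3% v 14.8% / 81.1%.
- Weibull shape 1.3: 3.1% / 95.2% v 3.9% / 91.6%.
- Progression dated at the next 8-weekly scan (interval from section 11; no deaths between scans assumed), with 10 and 20 months as true progression times: 12.3% / 92.5% v 18.8% / 92.7%.
- The same, with 10 and 20 months as scan-dated medians: 5.8% / 90.1% v 10.4% / 90.6%.

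**The case against.** The best defence is that the plan delivers what it promises. The only method 13.3 gives for PFS is Kaplan-Meier, and on that reading the rule gives about 9% and 86% against a stated 10% and 85%; the Wald replacement, at 8.5% and 90%, is further from both. Deriving a threshold from a parametric approximation and applying it to a Kaplan-Meier median is a defensible choice, and any two valid tests will disagree in some trials of 25 patients. The Kaplan-Meier estimate does not need exponential PFS, whereas the Wald decision does. Timing is largely covered by 13.1, 13.2 and section 14. Under scan dating the power gain disappears.

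Most of this stands, and it limits the point to a cheap improvement. Three things remain. The 14.5 figure itself comes from the exponential model, so keeping it does not free the rule from that assumption. The Wald test at the observed d had the lower type I error in every setting shown, with higher power except for a near tie under scan dating. And 13.1 is still silent on the estimator, on the unreached median and on the exact data cut.

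A reader might infer from the gap between 17.6 and 12 events that the trial runs at about 6.5% instead of 10% because of the fixed cut-off. The documents do not support that. The figure applies only to an exponential median, which no section specifies for the decision, and only about 2 points of the shortfall come from fixing the cut-off.

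**Conclusion.** The mismatch is real and its practical size is modest. The 14.5-month rule is the Wald test of 13.1 only at 12 events, while the planned cut expects 17.6 under the null. On the natural Kaplan-Meier reading the rule still has about 9% type I error and 86% power. It parts from the plan's own test in about 6% of null trials and 7% of alternative trials, and gives up about 4 points of power under the alternative.

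A reader might also infer that the rule inflates the error rate or breaks the design. It does not: under exponential PFS no reading examined exceeds 10%. Rates above 10% appear only under added assumptions (Weibull shape 0.8, scan dating). The Wald test also exceeds 10% at shape 0.8 and under one of the two scan-dating cases.

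These conclusions assume exponential PFS, uniform accrual, no dropout and a cut 12 months after last accrual; they change little with 15-month accrual.

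**What to change.** In section 13.1:

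- Set the primary analysis at 12 months after the last phase II enrolment.
- Decide with the Wald test at the observed number of events d: reject if ln(m/10)·√d ≥ 1.2816, where m = ln 2 × total PFS time / d. The cut-off is then 14.5 months at d = 12 and about 13.5 at d = 18.
- Restate the operating characteristics as about 8.5% type I error and 90% power under exponential PFS.
- Keep the Kaplan-Meier median and interval of 13.3 as descriptive.

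The downside is reliance on exponential PFS, as the stated power and the 14.5 figure already have. Neither rule holds 10% at Weibull shape 0.8 (about 14% v 15%). If progression is dated at 8-weekly scans, the gain is a type I error 4.6 to 6.5 points lower, not extra power.

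If the sponsor prefers the Kaplan-Meier rule, 13.1 should say so, say that an unreached median counts as at least 14.5 months, and state about 9% and 86%.

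Either way the cost is wording only: no extra patients or visits, and no follow-up beyond the 12 months already assumed.

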13.2 Sample Size, Accrual Rate and Study Duration

The planned sample size is between six and 18 patients in the phase I portion of the trial, and 25

patients in the phase II portion of the trial, for a total of 31 to 43 patients. The planned accrual rate is approximately 5 patients per quarter. Up to an additional one year of follow-up will be required for the last participant accrued to observe the patient's response and survival following therapy, for a total study length of about four years. Participants will be identified via targeted NextGen sequencing using the DFCI/BWH OncoPanel or another CLIA-certified method for genotyping.

Table 26: Accrual Targets					
Ethnic Category	Sex/Gender				
Zumie Cutegory	Females		Males		Total
Hispanic or Latino	0	+	1	=	1
Not Hispanic or Latino	15	+	27	=	42
Ethnic Category: Total of all subjects	15	+	28	=	43
Racial Category					
American Indian or Alaskan Native	0	+	1	=	1
Asian	0	+	0	=	0
Black or African American	0	+	0	=	0
Native Hawaiian or other Pacific Islander	0	+	0	=	0
White	15	+	27	=	42
Racial Category: Total of all subjects	15	+	28	=	43

13.3 Analysis of Primary and Secondary Endpoints

The primary and secondary analyses will include all eligible patients who started assigned therapy. The phase II evaluations will not include the patients enrolled to the phase I portion of this trial. The exception to this includes the planned analysis of toxicity data, which will include all patients who received study drug regardless of eligibility.

Overall response rate will be presented with a 90% exact binomial confidence interval. For a sample of size 25, the confidence interval will be no wider than 0.35. The distributions of overall survival and progression-free survival will be described using the method of Kaplan-Meier. Median PFS and OS will be summarized with 90% confidence intervals estimated using log (-log(endpoint)) methodology.

In the event that there are missing data points, no imputation of the missing data will be conducted.

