4. REGISTRATION PROCEDURES

4.1 General Guidelines for DF/HCC Institutions

Institutions will register eligible participants in the Clinical Trials Management System (CTMS) OnCore. Registrations must occur prior to the initiation of protocol therapy. Any participant not registered to the protocol before protocol therapy begins will be considered ineligible and registration will be denied.

An investigator will confirm eligibility criteria and a member of the study team will complete the protocol-specific eligibility checklist.

Following registration, participants may begin protocol therapy. Issues that would cause treatment delays should be discussed with the Overall Principal Investigator (PI). If a participant does not receive protocol therapy following registration, the participant's registration on the study must be canceled. Registration cancellations must be made in OnCore as soon as possible.

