13.4.2 Evaluation of the Primary Efficacy Endpoint

All eligible participants included in the study will be assessed for response, even if there are major protocol therapy deviations. Each participant should be assigned one of the following categories: 1) complete response, 2) partial response, 3) stable disease, 4) progressive disease, 5) early death from malignant disease, 6) early death from toxicity, 7) early death because of other cause, or 9) unknown (not assessable, insufficient data). By arbitrary convention, category 9 usually designates the "unknown" status of any type of data in a clinical database.

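### The phase II efficacy set drops treated patients found ineligible, with no rule that this be decided without knowledge of outcome; at about 12 events one or two such exclusions could change the result.

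*Combined protocol and SAP*

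**What the plan says.** Section 13.3 sets the efficacy population: "The primary and secondary analyses will include all eligible patients who started assigned therapy". The same paragraph makes an exception for toxicity, "which will include all patients who received study drug regardless of eligibility". Section 13.4.2 repeats the eligibility restriction for response: "All eligible participants included in the study will be assessed for response, even if there are major protocol therapy deviations". A therapy deviation therefore does not remove a patient from the efficacy analyses, but a finding of ineligibility does.

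Section 4.1 places the eligibility check at registration, before treatment: "An investigator will confirm eligibility criteria", and a checklist is completed. Section 1.1 describes the study as open-label, with a single-arm phase II part.

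The test is set out in section 13.1: "A sample of 25 subjects, with 12 observed PFS events, will have 85% power to detect an alternative median PFS of 20 months". On timing and the null: "We assume uniform accrual for 12 months, 12 additional months of follow-up, and a null median PFS of 10 months". The type I error is one-sided 10%, and the null is rejected at an observed median of 14.5 months or more.

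The plan does not say who may declare a treated patient ineligible, by when, or on what information. It provides no efficacy analysis in all treated phase II patients.

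**The concern.** The toxicity exception shows that the authors foresaw treated patients who turn out to be ineligible. Since eligibility is settled before treatment, removing such a patient means reopening that judgement afterwards, possibly when the patient's course is already known.

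Some criteria leave room for a second reading. Section 3.1.4 requires at least one lesion of 10 mm or more, using the short axis for nodes. Section 11.1.2 requires 15 mm or more in short axis for a node and calls nodes of 10 to under 15 mm non-measurable. A phase II patient whose only lesion is a 12 mm node is eligible under the first and arguably not under the second. Other criteria rest on judgement, such as uncontrolled intercurrent illness (3.2.7) and gastrointestinal impairment in the investigator's opinion (3.2.12).

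If exclusions fell on patients who progressed early, estimated PFS would lengthen and the comparison with a fixed 10-month null would favour the regimen.

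**Working it through.** **Inputs.** From section 13.1: 25 patients, 12 events, null median 10 months, alternative 20 months, 12 months of uniform accrual plus 12 of follow-up, one-sided 10% (z = 1.2816), and a Wald test on the log failure rate. Assumed, because the documents give no figure: exponential PFS, one or two exclusions, and progression at 2 months for those excluded in the worked cases.

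**Reproducing the plan.**
- Event probability with uniform accrual is 1 − (e^(−12λ) − e^(−24λ))/(12λ), with λ = ln 2/median. At 20 months this is 0.460, so 25 × 0.460 = 11.5 events (plan: 12). At 10 months it is 0.7045, so 17.6 events.
- Power = Φ(√d × ln 2 − 1.2816): 85.8% at 11.5 events and 86.9% at 12 (plan: 85%).
- Cut-off = 10 × exp(1.2816/√d): 14.48 months at 12 events (plan: 14.5), 14.72 at 11 and 15.0 at 10.

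The stated design is reproduced.

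**Fragility at 12 events.** The exponential median is ln 2 × T/d, where T is total follow-up in patient-months and d the number of events; z = √d × ln(median/10).

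| Analysis set | T | d | Median | z | One-sided p |
|---|---|---|---|---|---|
| All patients | 242.4 | 12 | 14.0 | 1.166 | 0.122, fail |
| One 2-month progressor dropped | 240.4 | 11 | 15.15 | 1.377 | 0.084, pass |
| All patients | 225.1 | 12 | 13.0 | 0.909 | 0.182, fail |
| Two 2-month progressors dropped | 221.1 | 10 | 15.3 | 1.350 | 0.089, pass |

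Both passes clear the fixed 14.5-month rule and also the cut-off recomputed for the remaining events (14.72 and 15.0). A change of result needs a full-set median in a band just below the cut-off. With the recomputed cut-off, that band starts at about 13.6 months for one removal and 12.7 for two. With the fixed 14.5 rule it starts at 13.4 and 12.3.

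**Type I error by simulation.** True median 10 months, 25 patients, analysis at 24 months:

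| Patients removed | Wald test | Kaplan-Meier median ≥ 14.5 |
|---|---|---|
| None | about 8.4% | 9.2% |
| Earliest progressor | about 12.8% | 9.5% |
| Two earliest progressors | about 18.2% | 17.7% |

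Repeat runs of the Wald test with all patients gave 8.4% to 8.5%. When one or two patients are removed without regard to outcome, the Wald error stays at 8.4% to 8.6%.

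**Cost of neutral exclusions.** With 24 or 23 patients, expected events under the alternative are 11.05 or 10.59, and power is 84.7% or 83.5%, against 85.8% with all 25.

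**The case against.** The best reply is that the criteria are mostly baseline facts: genotype, prior BRAF/MEK therapy, laboratory values, LVEF and QTc. They are checked at registration, and laboratory values are rechecked on cycle 1 day 1 if screening was more than 72 hours earlier (5.2.1). Major therapy deviations do not exclude anyone (13.4.2), and scans are read centrally (11.1.6). All of this stands and makes exclusions less likely. None of it controls how or when a treated patient may be declared ineligible; central reading protects the progression call, not the eligibility call.

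Several stronger readings are tempting, and the documents do not support them:
- *That the plan intends outcome-driven exclusion.* It does not. It leaves the route open, and it names no criterion whose late discovery would pick out early progressors.
- *That disease missed at baseline would be used to remove early failures.* Section 3.2.5 excludes only known untreated brain metastases, and section 11.1.3.3 counts a lesion at a site not scanned at baseline as progression. Such a patient stays in and contributes an event.
- *That any eligible-set median above 14.5 months shows significance.* That cut-off belongs to 12 events. At 10 events the Wald cut-off is 15.0.
- *That a single removal matters on every version of the test.* Section 13.1 rejects on an observed median and section 13.3 describes PFS by Kaplan-Meier. If the Kaplan-Meier median is the criterion, one removal barely moves the error rate, though two still do.
- *That different toxicity and efficacy sets are an inconsistency.* They answer different questions. The contrast shows only that treated but ineligible patients were foreseen.

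**Conclusion.** The point holds as a cheap improvement. Eligible-only analysis of PFS, OS and ORR, without a rule that ineligibility be decided in ignorance of outcome, leaves a small open-label test exposed to selection after treatment. At 12 events, one exclusion of an early progressor can turn a failed Wald test into a pass from a full-set median of about 13.6 months, and two can do so from about 12.7.

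The 12.8% and 18.2% error rates are ceilings. They require the excluded patients to be exactly the earliest progressors, and they rest on exponential PFS and an assumed one or two exclusions. A reader might take them as the trial's actual false-positive rate; the documents give no basis for that. If exclusions are unrelated to outcome, the Wald error is unchanged and the loss is one to two points of power.

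**What to change.** In sections 13.3 and 13.4.2, define the phase II PFS, OS and ORR population as all phase II patients who received any dose of protocol therapy, whatever is later found about eligibility. Report the eligible-only set as a sensitivity analysis. State that eligibility for that set is judged from baseline data only, by people without knowledge of the patient's outcome, and that each exclusion is listed with its reason. Reconcile the nodal size in 3.1.4 with 11.1.2 so that measurable disease has one meaning.

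Keeping the eligible set as primary, with the same outcome-blind rule and an all-treated sensitivity analysis, would also meet much of the concern. Making the all-treated set primary is simpler, because the primary result then depends on no later judgement.

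The cost is a few sentences and one extra table. The sample stays at 25 and computed power at 85.8%. The estimate may be slightly less favourable if ineligible patients do poorly.
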